9.4.1.1.1 Stopping Rules for Treatment With Siltuximab

Amgen will conduct evaluations of the treatment and outcome of the CRS events treated with siltuximab on an ongoing basis to assess if the threshold for pausing siltuximab treatment has been reached as outlined in the table below. If these stopping rules are met, an ad hoc DLRM will be triggered to review safety data and available PK, [REDACTED], and efficacy data. If recommended by DLRT, the use of siltuximab will resume. The stopping rules to trigger an adhoc DLRM to review siltuximab treatment use a Bayesian approach proposed by Thall et al, 1995; an adhoc DLRM will be triggered if the posterior probability that the CRS progression to grade 3 rate is greater than 30% is > 80% or the posterior probability that the CRS progression to grade 4 rate is greater than 10% is > 80%; or observation of any grade 5 CRS after the event has been treated with siltuximab. The stopping boundaries presented below assume a prior distribution of Beta (0.6, 1.4) for progression to grade 3 CRS and a prior distribution of Beta (0.2, 1.8) for progression to grade 4 CRS. The evaluations could occur more

frequently if necessary to address emerging safety concerns. If the triggered adhoc DLRM coincides with the regular DLRM, they may be combined.

Number of subjects treated with siltuximab	Trigger DLRM if severity of any CRS event treated with siltuximab progresses to Grade 5	
	Or this number of subjects with severity of CRS progressed to Grade 3 after being treated with siltuximab	Or this number of subjects with severity of CRS progressed to Grade 4 after being treated with siltuximab
5	≥ 3	≥ 2
10	≥ 5	≥ 3
15	≥ 7	≥ 3
20	≥ 8	≥ 4
25	≥ 10	≥ 5
30	≥ 12	≥ 5
35	≥ 13	≥ 6
40	≥ 15	≥ 6

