6.2.2 Dosage Adjustments, Delays, Rules for Withholding or Restarting, Permanent Discontinuation

6.2.2.1 Amgen Investigational Product: AMG 160

The reason for dose change of AMG 160 is to be recorded on each subject's electronic case report form (eCRF).

For treatment interruptions, delays, and discontinuations, refer to AMG 160 guidance in [Table 6-3](#) in consultation with the Amgen medical monitor.

If any of the following events occur, further accrual will be suspended and a safety analysis conducted and submitted to FDA for review prior to resuming enrollment.

- any 1 treatment-related grade 5 adverse event or
- any 2 of the same treatment-related, clinically significant grade 4 adverse events at least possibly related to AMG 160

6.2.2.1.1 Infusion Interruptions/Delays/Withholding and Re-start in Case of Technical/Logistical Issues

Events leading to infusion interruption or delay for technical/logistical reasons may include: technical problem with the infusion pump or the investigational product is incorrectly prepared or administered.

Infusion Interruptions due to Technical/Logistical Issues

The administration of AMG 160 should not be interrupted for short-term (approximately 60 minute) or [REDACTED], if possible. In case of infusion interruption, due to any technical or logistic reason, the interruption should be as short as possible and the infusion continued at the earliest time possible.

[figure not shown]
In case of infusion interruption, immediately consult with Amgen medical monitor to determine if:

- investigational product stability is sufficient to administer the remaining infusion or
- a new infusion can be administered or
- the dose should be withheld

For short-term (approximately 60 minute) infusions, if the remaining infusion can be administered, no specific precautions have to be taken. If a new infusion can be administered, follow the procedures in the Schedule of Activities (see Section 1.3) or the cycle day on which the original (interrupted) infusion was administered. [REDACTED]

[REDACTED] If the

infusion will need to be withheld, follow the instructions for re-start after interruptions due to adverse events described below for the next infusion.

Any interruption of an infusion should be recorded in the eCRF, providing the start and stop date/time of the infusion if the interruption is > 2 hours.

Infusion Delay due to Technical/Logistical Issues

[figure not shown]

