2	Symptoms require and respond to moderate intervention 
 Grade 1 CRS symptoms, AND Oxygen requirement < 40%, OR Hypotension responsive to fluids or low dose of 1 vasopressor^b, OR Grade 2 organ toxicity or grade 3 transaminitis per CTCAE criteria 	Immediately interrupt/delay AMG 160 until event improves to CRS grade ≤ 1. [REDACTED]	Administer: 
 Symptomatic treatment (eg, paracetamol/ acetaminophen for fever) Supplemental oxygen when oxygen saturation is < 90% on room air Intravenous fluids or low dose vasopressor for hypotension when systolic blood pressure is < 85 mmHg. Persistent tachycardia (eg, > 120 bpm) may also indicate the need for intervention for hypotension. Monitor for CRS symptoms including vital signs and pulse oximetry at least Q2 hours for 12 hours or until resolution to CRS grade ≤ 1, whichever is earlier. For subjects with extensive co-morbidities or poor performance status, manage per grade 3 CRS guidance below. Persistent tachycardia with complications (eg, atrial fibrillation) should be managed with rate control medications (eg, metoprolol) along with cardiology consultation. [REDACTED]	
 Re-start possible if successfully managed and improved to ≤ grade 1 within 7 days. Consult with Amgen medical monitor first. In case of infusion interruption, continue treatment with next planned dose (do not resume prior infusion). Delay of next infusion: 
 < 7 days: administer the delayed infusion (as long as the next scheduled infusion is > 6 days from delayed infusion) and follow the schedule of assessments for the cycle day on which the infusion was originally planned. > 7 days: skip the infusion and resume schedule of assessments for the next scheduled infusion Hospitalization: 48 hours Dose modification: resume at the same dose or reduce to next lower dose, if clinically indicated Additional measures: [REDACTED] and additional assessments as indicated in Section 6.2.2.1.2.4 	If there is no improvement to CRS ≤ grade 1 within 7 days OR If subject missed more than 2 consecutive doses of AMG 160

Abbreviations and footnotes defined on last page of table.

Table 6-3. Infusion Interruptions/Delays/Withholding/Permanent Discontinuation and Management of Adverse Events Including Dose Reductions

Grade	Description of Severity ^a	Interruption/Delay	Specific Management	Re-start guidance	Permanent Discontinuation

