Cytokine Release Syndrome (continued)					
3	Symptoms require and respond to aggressive intervention 
 • Grade 1 CRS symptoms, AND • Oxygen requirement \geq 40%, OR • Hypotension requiring high-dose^b or multiple vasopressors, OR • Grade 3 organ toxicity or grade 4 transaminitis per CTCAE criteria 	Immediately interrupt / delay AMG 160 until event improves to CRS grade \leq 1.	Admit to intensive care unit for close clinical and vital sign monitoring per institutional guidelines (unless related to asymptomatic elevation of liver enzymes). Administer [REDACTED] (or equivalent) IV at a dose maximum of 3 doses of 8 mg (24 mg/day). The dose should then be reduced step-wise. AND/OR Investigators should also consider use of tocilizumab ^{c,d,e} as an additional therapy in this setting at a dose of 4 - 8 mg/kg IV as a single dose. Persistent tachycardia with complications (eg, atrial fibrillation) should be managed with rate control medications (eg, metoprolol) along with cardiology consultation. [REDACTED]	
 • Re-start possible if successfully managed and improved to \leq grade 1 within 7 days. • Consult Amgen medical monitor. • In case of infusion interruption, continue treatment with next planned dose (do not resume prior infusion). • Delay of next infusion: 
 – < 7 days: administer the delayed infusion (as long as the next scheduled infusion is > 6 days from delayed infusion) and follow the schedule of assessments for the cycle day on which the infusion was originally planned. – > 7 days: skip the infusion and resume schedule of assessments for the next scheduled infusion • Hospitalization: 48 hours • Dose modification: reduce to next lower dose (continuation at same dose with [REDACTED] may be allowed – consult with medical monitor) Additional measures: [REDACTED] and additional assessments as indicated in Section 6.2.2.1.2.4	If there is no improvement to CRS \leq grade 1 within 7 days. OR If subject missed more than 2 consecutive doses of AMG 160 Decision to discontinue should be made in consultation with Amgen medical monitor.

Abbreviations and footnotes defined on last page of table.

Table 6-3. Infusion Interruptions/Delays/Withholding/Permanent Discontinuation and Management of Adverse Events Including Dose Reductions

Grade	Description of Severity ^a	Interruption/Delay	Specific Management	Re-start guidance	Permanent Discontinuation

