^b High dose vasopressors (all doses are required for ≥ 3 hours): Norepinephrine monotherapy ≥ 20 µg/min; Dopamine monotherapy ≥ 10 µg/kg/min, Phenylephrine monotherapy ≥ 200 µg/min, Epinephrine monotherapy ≥ 10 µg/min; If on vasopressin, vasopressin + norepinephrine equivalent of ≥ 10 µg/min; If on combination vasopressors (not vasopressin), norepinephrine equivalent of ≥ 20 µg/min

- ^c All sites will ensure that CRS rescue medications are available on-site, including corticosteroids and (for sites in regions where tocilizumab is approved and available, eg, the US and Germany) 2 doses of tocilizumab per study subject
- ^d If tocilizumab is not available, siltuximab (an anti-IL-6 monoclonal antibody) may be used in the management of cytokine release syndrome, following the criteria outlined in the Management of Adverse Events table. The recommended dose of siltuximab is 11 mg/kg administered over 1 hour as an intravenous infusion, consistent with the prescribing information for the treatment of multicentric Castleman's disease (Sylvant Prescribing Information), and the CARTOX Working Group Guidelines for CRS management (Neelapu, 2018). Siltuximab may be repeated if needed, in the event that CRS recurs after a subsequent infusion of AMG 160. Siltuximab may not be repeated in an individual subject that develops anaphylaxis to siltuximab, or gastrointestinal perforation after siltuximab.
- ^e A subgroup analysis for subjects treated with siltuximab will be evaluated, including CRS outcomes, safety, and PK data.

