9.4.1 Planned Analyses

9.4.1.1 Interim Analysis and Early Stopping Guidelines

Safety data will be reviewed on an ongoing basis.

During dose exploration and formally during DLRMs, Amgen, in consultation with the site investigators, will review all available cumulative data by cohort prior to making dose escalation or dose de-escalation recommendations. Adverse events and DLTs observed in all subjects will be evaluated continually and fully integrated into all DLRMs and considered in all enrollment and dosing decisions. During dose expansion, Amgen will conduct evaluations of the ongoing grade 4 or higher treatment-related adverse event rate to assess if the threshold for possible early trial termination has been reached. If this threshold is met, enrollment to dose expansion will be halted pending review of safety data by the DLRT. After receiving the DLRT recommendation, Amgen will choose to take one of the following actions.

- 1) Terminate the trial

- 2) Amend the protocol to potentially improve the benefit/risk for subjects (eg, increase safety monitoring, modify dose/schedule, mandate [REDACTED])
- 3) Continue dose expansion without any changes

The stopping rules use a Bayesian approach proposed by Thall et al, 1995 to terminate the study if the posterior probability that the grade 4 or higher treatment-related adverse event rate is greater than 20% is $> 80\%$. The stopping boundaries assume a prior distribution of Beta (0.40, 1.60) are presented in [Table 9-1](#) and the operating characteristics with pre-specified batch size of 10 new subjects per batch are presented in [Table 9-2](#). The operating characteristics in [Table 9-2](#) provide the probability of stopping the trial early for given hypothetical true rate of grade 4 or higher treatment-related adverse events, whereas the stopping criteria in [Table 9-2](#) are based on situations where the empirical evidence would result in a posterior probability of $\geq 80\%$ that the true grade 4 or higher treatment-related adverse event rate is $\geq 20\%$.

Table 9-1. Stopping Boundary for Dose Expansion With Posterior Probability of 80% and Grade 4 or Higher Treatment-related Adverse Event Limit of 20%

Number of Subjects	Stop Study if Observing These Many Grade 4 or Higher Treatment-related Adverse Events
10	≥ 4
20	≥ 6
30	≥ 9
40	Dose Expansion Complete

Table 9-2. Operating Characteristics With Batch Size of 10 Subjects

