
Recording Adverse Events and Serious Adverse Events

Adverse Event and Serious Adverse Event Recording

- When an adverse event or serious adverse event occurs, it is the responsibility of the investigator to review all documentation (eg, hospital progress notes, laboratory, and diagnostics reports) related to the event.
- The investigator will then record all relevant adverse event/serious adverse event information in the Event case report form (CRF).
- The investigator must assign the following adverse event attributes:
 - Adverse event diagnosis or syndrome(s), if known (if not known, signs or symptoms);
 - Dates of onset and resolution (if resolved);
 - **Assessment of seriousness;**
 - Severity (or toxicity defined below);
 - assessment of relatedness to investigational product, other protocol-required therapies, and/or study-mandated procedure including ⁶⁸Gallium (⁶⁸Ga)- prostate-specific membrane antigen (PSMA)-11, and
 - Action taken.
- If the severity of an adverse event changes from the date of onset to the date of resolution, record a single event for each level of severity on the Event CRF.
- It is not acceptable for the investigator to send photocopies of the subject's medical records to Amgen in lieu of completion of the Event CRF page.
- If specifically requested, the investigator may need to provide additional follow-up information, such as discharge summaries, medical records, or extracts from the medical records. In this case, all subject identifiers, with the exception of the subject number, will be blinded on the copies of the medical records before submission to Amgen.

- The investigator will attempt to establish a diagnosis of the event based on signs, symptoms, and/or other clinical information. In such cases, the diagnosis (not the individual signs/symptoms) will be documented as the adverse event/serious adverse event.

Evaluating Adverse Events and Serious Adverse Events

Assessment of Severity

The investigator will make an assessment of severity for each adverse event and serious adverse event reported during the study. The assessment of severity will be based on:

The **Common Terminology Criteria for Adverse Events**, version 5.0 which is available at the following location:

http://ctep.cancer.gov/protocolDevelopment/electronic_applications/ctc.htm.

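### Read literally, the siltuximab rule's grade 3 count leaves out subjects who reach grade 4 with no grade 3 step, so it can respond less to a worse outcome (small effect, optional fix)

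*Protocol*

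**What the plan says.** Protocol 9.4.1.1.1 has three triggers for an ad hoc dose level review meeting on siltuximab.

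- **Grade 3:** posterior probability above 80% that "the CRS progression to grade 3 rate is greater than 30" percent, with prior Beta(0.6, 1.4). The table column reads "Or this number of subjects with severity of CRS progressed to Grade 3 after being treated with siltuximab".
- **Grade 4:** posterior probability above 80% that the rate of progression to grade 4 exceeds 10%, with prior Beta(0.2, 1.8) and its own column.
- **Grade 5:** any single case after siltuximab.

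SAP 7.1.1 repeats the table and the grade 3 statement. Neither document says *or higher* in either column. The dose-expansion safety rule in Protocol 9.4.1.1 does say it; it covers "evaluations of the ongoing grade 4 or higher treatment-related adverse event rate".

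On who receives siltuximab, footnote d of Protocol Table 6-3 states "If tocilizumab is not available, siltuximab (an anti-IL-6 monoclonal antibody) may be used in the management of cytokine release syndrome". The grade 3 CRS row of that table states "Investigators should also consider use of tocilizumab". The grade 2 row adds "For subjects with extensive co-morbidities or poor performance status, manage per grade 3 CRS guidance below". Part of the grade 2 row is redacted.

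**The concern.** A subject given siltuximab at grade 3 who then worsens goes to grade 4. So does a subject who jumps from grade 2 to grade 4. Neither passes through grade 3 after treatment, so on the literal wording each is a non-event in the 30% model and counts only in the grade 4 column. Replacing a grade 3 progression with a grade 4 progression can then turn a trigger into no trigger. A stopping rule for a rescue treatment should not become quieter as outcomes worsen.

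The gap is limited to subjects with no grade 3 step. For changes in severity, Protocol Appendix 4 (11.4) asks sites to "record a single event for each level of severity on the Event CRF", so a subject who goes 2 to 3 to 4 has a grade 3 record and can count in both columns.

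At stake is the timing of a review meeting and of a reversible pause in siltuximab use.

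**Working it through.** **Inputs.** The priors, limits, 80% cut-off and boundaries come from Protocol 9.4.1.1.1. True rates, grade at treatment and the number of siltuximab users are not in the documents; where used below they are assumptions.

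**Step 1: reproduce the plan's boundaries.** For n treated subjects, find the smallest x with

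- grade 3: P(p > 0.30 | Beta(0.6 + x, 1.4 + n − x)) > 0.80
- grade 4: P(p > 0.10 | Beta(0.2 + x, 1.8 + n − x)) > 0.80

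| n | 5 | 10 | 15 | 20 | 25 | 30 | 35 | 40 |
|---|---|---|---|---|---|---|---|---|
| Grade 3, ≥ | 3 | 5 | 7 | 8 | 10 | 12 | 13 | 15 |
| Grade 4, ≥ | 2 | 3 | 3 | 4 | 5 | 5 | 6 | 6 |

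All 16 agree with the printed table.

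**Step 2: the case n = 5.**

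- Three subjects progress to grade 3: posterior 0.87, so a review is triggered.
- Two progress to grade 3 and one goes directly to grade 4, read literally: the grade 3 model sees 2/5 (0.63) and the grade 4 model sees 1/5 (0.63). There is no trigger.
- The same three subjects counted as grade 3 or higher: 3/5 gives 0.87, so a review is triggered.

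This is the only split at n = 5 where the two readings differ.

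**Step 3: largest total at grade 3 or 4 without a trigger.** The literal maximum is (grade 3 boundary − 1) + (grade 4 boundary − 1). With *or higher* it is grade 3 boundary − 1.

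- n = 5: 2 + 1 = 3 versus 2
- n = 10: 4 + 2 = 6 versus 4
- n = 15: 6 + 2 = 8 versus 6
- n = 20: 7 + 3 = 10 versus 7

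From n = 10 these literal worst cases contain at least two grade 4 CRS events. Protocol 6.2.2.1 suspends accrual after "any 2 of the same treatment-related, clinically significant grade 4 adverse events at least possibly related to AMG 160", so another rule would normally act. Allowing at most one grade 4 event, the literal worst cases are 3/5, 5/10, 7/15 and 8/20, each one subject above the *or higher* maximum. Their posteriors for grade 3 or higher are 0.87, 0.88, 0.89 and 0.81.

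**Step 4: how often it would matter.** The simulation used 400,000 sequences with looks every five subjects and no grade 5. Assumptions: of subjects treated below grade 3, 40% reach exactly grade 3 and 10% reach grade 4 through grade 3; of subjects treated at grade 3, 15% reach grade 4. Chance of a siltuximab trigger by n = 10:

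| Share treated at grade 3 | Literal | *Or higher* | Difference (points) |
|---|---|---|---|
| All | 24% | 24% | 0 |
| Three quarters | 22% | 24% | 2 |
| Half | 28% | 34% | 6 |
| A quarter | 45% | 51% | 6 |
| None | 70% | 70% | 0 |

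If two or more grade 4 CRS events among siltuximab-treated subjects are also counted as an action (accrual suspension), the half-and-half case is 44% versus 47%, the three-quarters case is about 42% versus 43%, and the range over the mixes is 0 to 3 points.

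If all subjects are treated at grade 3, the grade 4 boundary is lower at every look and fires first, so the wording has no effect.

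**The case against.** The best defence is that the plan sets three parallel tiers on purpose. Grade 4 is monitored under a stricter 10% limit with a lower boundary, and any grade 5 triggers. A subject treated at grade 3 cannot progress to grade 3, and the grade 4 column asks the right question for that subject. The contrast with 9.4.1.1 is weak evidence of an omission: that rule has one tier and no separate grade 5 trigger, so it needs the cumulative wording. This stands as far as it goes. Separate limits may have been intended, but the text does not say how a grade 4 case without a grade 3 step counts.

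A reader might infer that the rule stays silent although its own 80% criterion is met. The documents do not support that. The stated criterion concerns progression to grade 3; the 0.87 comes from applying the plan's prior and limit to a broader event.

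A reader might also infer a large loss of sensitivity. With assumed rates of 30% worst grade 3 and 10% worst grade 4, the trigger chance by n = 10 is 33% literal versus 47% with *or higher*, but only if every grade 4 case skips grade 3. Nothing in the documents supports that assumption.

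Other safeguards also limit the harm. Safety review is ongoing, siltuximab evaluations may be made more often, a grade 4 event within 28 days is a DLT unless clearly due to another cause, and grade 4 CRS permanently ends AMG 160. Accrual suspension does not itself pause siltuximab, and it does not act on the n = 5 case, which has one grade 4 event.

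Finally, *or higher* does not give a clean rate. Table 6-3 also places tocilizumab at grade 4, and subjects first treated there remain in the denominator as non-events in both columns under either wording.

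**Conclusion.** The point holds as a small, optional wording correction to the grade 3 column. Read literally, the rule can respond less to a worse outcome, shown exactly by the n = 5 case. That result depends only on the plan's own priors, limits and boundaries and on the literal reading.

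The practical size is 0 to 6 percentage points in the chance of a trigger by ten treated subjects, or 0 to 3 counting accrual suspension. These figures rest on assumed rates and mixes. The gap needs some subjects who reach exactly grade 3 and others who reach grade 4 without that step. The visible text allows both, but the redaction in the grade 2 row means the actual mix cannot be judged. Siltuximab is only a substitute when tocilizumab is unavailable, so reaching ten users is itself uncertain. The consequence is a delayed review meeting.

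**What to change.** In Protocol 9.4.1.1.1 and SAP 7.1.1, change the grade 3 column and its posterior statement to *progressed to Grade 3 or higher*. Count each subject at the worst CRS grade after siltuximab if that is above the grade at treatment. Keep the priors, the 30% and 10% limits and all printed boundaries. The grade 4 column needs no change, because any grade 5 already triggers a review.

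If the 30% limit was meant for grade 3 alone, say so and state how a grade 4 case without a grade 3 step is counted.

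The cost is a wording change in two documents and slightly more ad hoc reviews: at assumed rates of 20% worst grade 3 and 5% worst grade 4, at most 15% versus 10% by n = 10. If separate limits were intended, the new wording tightens the rule.
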